Quantifying the Influence of Yogic Breathwork on Cerebrospinal Fluid Circulation

Unique Protocol Identification Number: STUDY00019281

National Clinical Trial (NCT) Identified Number: NCT03858309

Principal Investigator: [name]

Sponsor: Oregon Health & Science University

Grant Title: Quantifying the Influence of Yogic Breathwork on Cerebrospinal Fluid Circulation

Grant Number: K99AT010158

Funded by: NCCIH

November 11 2019

Principal Investigator or Clinical Site Investigator:

Name: [name]
Title: Senior Research Associate

Investigator Contact Information:

Affiliation: Oregon Health & Science University
Address: [name]
[contact]
Email: [contact]

1) Protocol Title

Quantifying the Influence of Yogic Breathwork on Cerebrospinal Fluid Circulation

2) Objectives

The purpose of this protocol is to determine the influence of an 8-week yogic breathwork intervention on cerebrospinal fluid (CSF) dynamics among healthy subjects using a non-invasive magnetic imaging (MRI) technique. We will examine this aim by studying the changes in each subject's pre- and post-intervention CSF dynamics using the non-invasive RT-PCMRI technique during two MRI scans (one before and one after the 8-week intervention). This aim will test the hypothesis that a regular yogic breathwork practice will enable participants to sustain slow and rhythmical breathing patterns and create larger modulations in their CSF dynamics.

3) Background

Yogic breathwork (YB) is an appealing mind-body therapy for healthcare management purposes because it is a low-risk and low-cost practice that can be easily learned and performed without any additional equipment. It is important to understand the mechanisms for the benefits of YB practices. Based on our preliminary results, we believe that another - less explored- potential mechanism for the positive effects of YB can be its direct influence on cerebrospinal fluid (CSF) circulation, which to date has not yet been quantified due to lack of non-invasive methodology.

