CSF circulation. CSF, a clear colorless fluid secreted by the choroid plexuses, moves by bulk flow (*macrocirculation*) around the central nervous system (CNS), and ensures the health of the CNS⁶. Impaired CSF circulation can comprise the normal physiological functions of the CNS, which then may contribute to CNS diseases including neurodegenerative conditions⁷. Furthermore, CSF circulation plays a key role in maintaining glymphatic transportation of CSF (*microcirculation*). Recent research efforts^{8,9} have defined a "*glymphatic function*", a brain-wide clearance mechanism facilitates the clearance of solutes and metabolic wastes from the brain interstitium. Sleep and arousal state are critical regulators of glymphatic function, since CSF tracer influx and interstitial solute clearance are increased during both sleep and anesthesia compared to the wakefulness¹, which is associated with slowed amyloid beta clearance and more rapid amyloid plaque deposition². The impairment of glymphatic function underlies the development of CNS diseases in the aging brain remains unknown, so it is critical to better understand the complete mechanisms supporting CSF circulation in the human CNS by i) developing non-invasive approaches to measure CSF circulation, and ii) potentially identifying therapies that can regulate and enhance CSF circulation. For this aim, we recently developed novel non-invasive imaging approaches to quantify CSF dynamics ¹² and we aim to study YB as a potential therapy for regulating and enhancing CSF circulation.

4) Study Design

This study is the K99 phase of the NIH-NCCIH K99/R00 study K99AT010158.

Protocol. The study protocol consists of 20 healthy young subjects undergoing an 8-week intervention (10 subjects in arm 1 and 10 subjects in the active control arm 2), and outcome measures within a 2-week period of pre-and post-intervention. We will test the hypothesis that the yogic breathwork practice with sophisticated breathing practices, compared to active control will enable participants to sustain slow and rhythmical breathing patterns and create larger modulations in their CSF dynamics.

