Optimization Scans: In order to optimize the study MRI protocol, we will implement optimization scans with healthy volunteers (18-65 y-o) who will only undergo ~1-hour optimization scans including the non-invasive MRI scan (which is to be optimized for the study intervention scans). We have included a separate consent form for the optimization scan volunteers. Optimization scans will be conducted with healthy population (18-65 y-o).

Interventions. YB protocol will incorporate a set of yogic breathing practices that will create larger

modulations in CSF dynamics. Active control protocol will include slow breathing. Both 8-week interventions will consist of 60-minute weekly group on-site sessions (1 day/week) with a 20-minute daily home sessions (in between on-site sessions; 6 days/week) using home-aid practice materials. We will define a benchmark of at least 8 on-site sessions and 15-min daily^{13,14} home practice (4 days/week) in order to see the effects we propose. We will objectively track subjects' respiration using a wearable device, e.g., Spire¹⁵ or Oura ring¹⁶. We plan to buy one of each and pilot each for 2 weeks on several study team members to assess prior to the interventions. In addition, subjects will be instructed to report the frequency and duration of their daily home practice in a logbook provided. We have tested the Spire³ health tag and Fitbit tracker, and plan to include in the protocol to objectively determine subjects' home practice. Participants may have one or both of these devices for the study team to track participant's home practice.

Interventionists. The YB and the control intervention will be guided by two separate certified experienced yoga teachers. Prior to being involved in the study and guiding the study interventions, the two interventionists will go through the necessary trainings for human subject research and IRB protocol.

Outcome measures will be i) blood pressure, ii) body mass index (BMI), iii) CSF flow velocities measured with the non-invasive MRI technique during ~1-hour MRI scans, iv) physiological data from wearable devices. We will also review response to self-report questionnaires.

5) Study Population

a) Number of Subjects

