- We will assess each subject's response to the following self-report questionnaires during their imaging visits: quality of life (Short-Form Health Survey; SF-36¹⁷), sleep quality (Pittsburgh Sleep Quality Index; PSQI¹⁸), perceived stress (Perceived Stress Scale; PSS¹⁹), Positive Affect Negative Affect Scale - Expanded (PANAS-X)²⁰, The Patient-Reported Outcomes Measurement Information System (PROMIS)²¹, and Cognitive and Affective Mindfulness Scale-Revised (CAMS-R)²². Additionally, we will assess subject's attitudes, expectancy and blinding towards the study.

Physiological Data Tracking:

- **Respiration:** Each subject will be provided with a wearable device in order for the study team to objectively track subject respiration, thus home practice, throughout the intervention. For this purpose, we will use a commercial off the shelf monitor (Spire³). Study staff will assure that these devices remain free of potential identifiers. We will create a respiration tracker account for each user. Subjects will receive instructions on how to utilize the wearable device during the first imaging session.
- **Sleep:** A sleep tracking methodology may be implemented within the study to investigate the effects of the intervention on long-term sleep patterns – using a Fitbit tracker. Study staff will assure that these devices remain free of potential identifiers, and will create a sleep tracking account for each subject. Subjects will receive instructions on how to utilize the wearable device during the first imaging session.

Randomization. Subjects will be told they will be enrolled in one of the 8-week intervention groups for a set of breathing practices. Group allocation will be performed through a sex and age-based randomization by a study team member who will inform the subjects with which group they will be enrolled in. Neither the subject nor the investigator can choose which group the subject will be in. Subjects will be instructed and reminded not to reveal what group they are in during the study assessment visits. They will be instructed to ask the investigator if they have any questions about this kind of study.

i. 8-week interventions.

Breathing practices:

- The yogic breathwork protocol will incorporate breathing practices that will create slow deep rhythmical and large CSF flow patterns. Active control protocol will include slow breathing practices.

Interventions:

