Post-acquisition, each data set will be examined for quality and completeness by the trained study team.

CSF flow:

- CSF flow data analysis will be performed using a semiautomated pulsatility-based segmentation procedure. The velocity waveform will be averaged over the highly correlated ROI pixels. The maximum and minimum peak values of the averaged CSF flow velocities will then be used for analysis (see details below *Statistical Analysis*).
- The respiration frequency band and the cardiac frequency band will be defined based on the two main distinct peak amplitudes of the frequency spectrum of the averaged CSF velocity waveforms measured with RT-PCMRI.
- The relative contribution of the respiration versus cardiac component of the CSF velocity waveforms will then be quantified by defining a power ratio between respiratory component and the cardiac component.

Respiration and ECG data:

- The pulse ox and respiration data collected during the RT-PCMRI acquisitions will be filtered using a 4th order Butterworth to extract only the respiration and only cardiac component.

Wearable device:

- Respiration data from wearable device collected during the 8-week intervention will be analyzed for the respiration rate and peak-to-peak respiration intervals. If collected, sleep data measured with wearable device will be analyzed to measure the influence of intervention on participants' long-term

sleep patterns objectively.

Self-report questionnaires:

- Response to self-report questionnaires will be analyzed for the statistical analysis to compare the changes in subject's quality of life, sleep, and existing stress levels.

Statistical Analysis

- The major dependent variables will be i) CSF flow metrics maximum and minimum (values of average CSF velocities; relative ratio of respiration vs. cardiac component of the CSF velocity; ratio of the maximum CSF velocity during breathing practices to the average of peak CSF velocities at baseline during natural breathing, ii) respiration rate and peak-to-peak respiration intervals and iii) self-reported questionnaire results. The effects of the interventions on these variables will be tested in a multivariate analysis of variance with repeated measures to compare pre- and post-intervention. An alpha value of 0.05 will be used for statistical significance.

9) Privacy, Confidentiality and Data Security

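### Section 8 names only a pre/post contrast, which does not test the section 4 hypothesis against active control; name the arm-by-time term and align sections 2, 4 and 8

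*Combined protocol and SAP*

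**What the plan says.** Section 4 (Study Design, Protocol) sets out two arms, "10 subjects in arm 1 and 10 subjects in the active control arm 2", and states this hypothesis: "yogic breathwork practice with sophisticated breathing practices, compared to active control will enable participants to sustain slow and rhythmical breathing patterns". It adds that CSF modulations are expected to be larger. Section 6 (Randomization) adds: "Group allocation will be performed through a sex and age-based randomization by a study team member". Section 4 (Interventions) describes the comparator: "Active control protocol will include slow breathing".

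Section 2 (Objectives) gives the hypothesis without a comparator. The aim will "test the hypothesis that a regular yogic breathwork practice will enable participants to sustain slow and rhythmical breathing patterns", and it is examined through changes in each subject's "pre- and post-intervention CSF dynamics using the non-invasive RT-PCMRI technique during two MRI scans".

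Section 8 (Statistical Analysis) is the only text that names a statistical test. It lists CSF flow metrics, respiration measures and questionnaire results, and says that the effects of the interventions on them will be "tested in a multivariate analysis of variance with repeated measures to compare pre- and post-intervention", at alpha 0.05. It names no arm factor, arm-by-time term or between-arm difference. The questionnaire and wearable-device paragraphs of section 8 name none either.

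**The concern.** Section 4 asks whether yogic breathwork does more than slow breathing. The contrast named in section 8 asks whether subjects differ after 8 weeks from before. These are different questions, and a yes to the second is compatible with two arms that changed equally.

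Equal change is plausible here because the control is not inert: it also trains slow breathing, on the same weekly and home schedule. If the pre/post contrast were used as the test, a significant result could be reported as support for yogic breathwork without any evidence that it adds to slow breathing. Section 2 frames the aim as within-subject change with no comparator, which makes the time-only reading of section 8 a natural one.

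**Working it through.** **Inputs.** From the documents: 10 per arm (section 4), possibly 13 per arm (section 5a), alpha 0.05 (section 8), one scan before and one after the intervention (section 2). The documents give no effect size, SD, correlation or power, so there is no planned figure to reproduce. The following are assumptions: two-sided tests, effects in SD units of the change score, and the effect sizes and correlations shown.

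**A. Both arms change equally by d SD, so the section 4 hypothesis is false.**

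- Pooled pre/post test, n = 20: noncentral t, df 19, noncentrality d√20 = 1.34, 2.24, 3.58 for d = 0.3, 0.5, 0.8.
- Yogic arm alone, n = 10: df 9, noncentrality d√10 = 0.95, 1.58, 2.53. Call the resulting power p.
- Yogic arm significant and control arm not: p(1 − p), since the arms are independent and have the same p. At d = 0.5 this is 0.293 × 0.707 = 0.207.
- Between-arm test: with two time points, the arm-by-time test on one outcome is a two-sample t-test on the change scores. Its null hypothesis is true here.

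| Assumed equal change (SD) | 0.3 | 0.5 | 0.8 |
|---|---|---|---|
| Pooled pre/post significant | 25% | 56% | 92% |
| Yogic arm alone significant | 14% | 29% | 62% |
| Yogic significant, control not | 12% | 21% | 24% |
| Between-arm test significant | 5% | 5% | 5% |

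Simulation of 200,000 trials gave 11.7%, 20.9% and 23.6% for the third row, and 5.0%, 5.1% and 4.9% for the fourth. Keeping arm in the model while testing time (df 18) leaves the first row unchanged after rounding. Separate tests within each arm do not solve the problem, as the third row shows.

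**B. Power of the between-arm test, one outcome, true arm difference in change of Δ SD.** Noncentrality is Δ√(n/2), df 2n − 2.

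- n = 10, Δ = 0.8: 0.8 × √5 = 1.79, df 18, power 0.395.
- n = 13 with all retained, Δ = 0.8: 0.8 × √6.5 = 2.04, df 24, power 0.499.
- 80% power at n = 10 needs Δ = 1.32.
- 95% CI half-width at n = 10: 2.101 × √(2/10) = 0.94 SD.

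**C. Power of the joint arm-by-time test of the four CSF metrics, 10 per arm.** This is Hotelling's T² on change scores, F(4, 15), noncentrality (10/2)D² = 5D². With common correlation ρ, D² = Δ²(1 + 2ρ)/[(1 − ρ)(1 + 3ρ)] if one metric differs, and 4Δ²/(1 + 3ρ) if all four do. At Δ = 0.8:

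| ρ | D², one differs | Power | D², all four differ | Power |
|---|---|---|---|---|
| 0 | 0.64 | 20% | 2.56 | 69% |
| 0.5 | 1.02 | 30% | 1.02 | 30% |
| 0.7 | 1.65 | 48% | 0.83 | 25% |

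Independence is not a likely case. Maximum CSF velocity is one of the four metrics, and a maximum CSF velocity is also the numerator of another.

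**The case against.** The strongest reply is that the arm comparison is already there. Section 4 names it as the hypothesis, section 8 speaks of the effects of the interventions in the plural, and a repeated-measures MANOVA routinely has arm as a between-subject factor. All of that stands. A reader might infer that the plan excludes a comparison between arms, and the documents do not support that. What they show is that the analysis text names one contrast, and it is not the one that decides the stated hypothesis.

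A reader might also infer that section 8 leaves open which outcomes enter the test. It does not: the MANOVA is applied to the variables just listed. Nor does the text fix how many scores that means. Section 6 plans to assess "response to the following self-report questionnaires during their imaging visits" and then names six instruments, but any count depends on how many scores each contributes.

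A third reply is that this is a small study. Section 5a speaks of intervention development and of judging instruments and participant burden. That lowers what one should expect of power, but it does not make a pre/post contrast an answer to a between-arm question. Finally, section 2 lacks a comparator without contradicting section 4, so the change there is alignment, not correction of an error.

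**Conclusion.** The point holds as a mismatch between hypothesis and named contrast, and should be fixed before analysis. Followed literally, section 8 would give a significant result in 25% to 92% of trials in which yogic breathwork adds nothing to the control, for equal true changes of 0.3 to 0.8 SD. Those rates rest on assumed effects and on pooling the arms. The 5% rate for the between-arm test does not depend on the size of the common change. The right test lies within the method already chosen, so the fault is one of specification and not of design. Naming that test does not make it powerful: with 10 per arm, only differences of about 1.3 SD on a single outcome reach 80% power.

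**What to change.** State in section 8:

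> The section 4 hypothesis is tested by the arm-by-time term of the repeated-measures MANOVA (the between-arm difference in change, Visit 11 minus Visit 2) at alpha 0.05, on the section 8 outcomes measured at both visits, including the CSF flow metrics and the respiration measures taken during MRI. For each outcome, the signed difference in change (yogic breathwork minus active control) is reported with a 95% confidence interval. Within-arm changes are descriptive. A non-significant result does not show that the arms are equal.

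Both CSF and breathing must be covered because the section 4 hypothesis has both parts. Table 1 schedules physiological measures during MRI at Visits 2 and 11 but wearable tracking only at Visits 3-10, so the breathing part needs the MRI recordings. The signed differences are needed because the joint term has no direction, while the hypothesis says larger.

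Add the comparison with active control to the section 2 hypothesis, so that sections 2, 4 and 8 agree.

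The cost is wording only; no visits or measurements are added. The downside is low power. At an assumed 0.8 SD arm difference, one outcome has about 40% with 10 per arm, or 50% if 13 per arm are recruited and all retained. The joint test of the four CSF metrics has about 20% to 69% with 10 per arm. Each outcome in a joint test also takes one denominator degree of freedom (19 − p for p outcomes in 20 subjects), so the number of questionnaire scores should be settled before the test is run.
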